This proposal unites neuroimagers, experts in conducting and analyzing human PET studies with behavioral scientists, experts in developing and testing treatments for alcoholism. We will conduct the first-ever *in vivo* PET imaging study of KOR and NTX occupancy in two cohorts of HD (18 FHP and 18 FHN) and relate our imaging findings to FH and alterations of drinking behavior by NTX in the ADP. Through this work, we will advance our understanding of (a) the degree of involvement of the kappa system in reducing drinking in humans by NTX, (b) the contribution of FH to this relationship, and (c) refine the use of a new PET imaging tracer. In so doing, we will inform the development of future targeted pharmacotherapies for alcoholism and lay the groundwork for other important investigations into the KOR/dynorphin system *in vivo*.

Primary (P), Secondary (S), and Auxiliary (A) Specific Aims:

- P1. **Occupancy of KOR by NTX and drinking:** To determine the degree to which occupancy of KORs by a 100 mg/day dose of NTX mediates (influences the strength of) responsivity to NTX treatment in all heavy drinkers. It is expected that KOR occupancy will significantly mediate the relationship between NTX treatment and responsivity. „Responsivity“, measured via ADP, is the change in number of drinks consumed at the baseline ADP vs. NTX ADP.
- P2. **Family History of Alcoholism as a moderator:** To determine whether the relationship between NTX responsivity and occupancy of KOR is different in FHP vs. FHN heavy drinkers.
- P3. To determine if baseline KOR availability differs between heavy drinkers and healthy control socialdrinkers

S1. **Baseline KOR differences**

- a. To determine if baseline levels of KOR differ between FHP and FHN heavy drinkers.
- b. To determine if baseline KOR level is related to either baseline drinking or responsivity to NTX.

S2. **Identify and validate a reference region** (area devoid of specific binding) for our new KOR tracer. A reference region would simplify PET analysis.

S3. **Optimize the scan duration** for clinical populations being imaged with the new KOR tracer.

Shorter scans would increase compliance and decrease discomfort to subjects.

A1. **Relationship to other behavioral measures:** To determine if occupancy of KORs is related to measures of alcohol craving, stimulation or sedation, assessed in the ADP.

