activation of KOR results in decreased dopamine release in brain reward areas [13, 14]. The potential role of KORs in mediating alcohol drinking behavior has been the focus of several studies in animals and humans. Mice that lack the KOR drink more alcohol and have greater release of dopamine in response to alcohol [15]. Rodents with an increased propensity to consume alcohol have lower dynorphin levels in several brain regions that are involved in the control of alcohol drinking [16-18]. In humans, the presence of the OPRK1 allele (which decreases expression of KOR) is associated with increased risk of alcoholism [19]. The above evidence suggests that differences in the status of the KOR system may mediate differences in propensity to drink alcohol. The current proposal will be the first to compare KOR occupancy in FHP and FHN drinkers and correlate KOR levels with drinking in the ADP.

The effect of stimulating or inhibiting the KOR opioid system on alcohol drinking appears to depend, in part, on the prior history of alcohol exposure. In alcohol naïve animals, stimulation of KOR by agonists decreases alcohol drinking [20], while inhibition of KOR by antagonists increases alcohol drinking [21]. Chronic alcohol exposure dysregulates the dynorphin/KOR system; specifically, dynorphin levels are enhanced and number of KOR are reduced [22, 23]. The aversive effect of dynorphin/KOR activation is decreased in individuals whose dynorphin/KOR system has been chronically stimulated, such as those with chronic pain or those with a long history of polysubstance abuse, which may reflect a reduced number or binding of KOR's [24, 25]. In contrast to the above evidence, in alcohol dependent animals, KOR antagonists reduce alcohol drinking [26], suggesting that chronic alcohol drinking also alters the KOR system. The above evidence suggests that differences in the KOR system may mediate differential responsivity to NTX.

The proposed project would be the first to assess the potential contribution of the KOR system to individual differences in naltrexone-mediated changes in alcohol drinking using an established ADP in alcohol dependent, heavy drinkers (HD). Additionally, the current proposal will be the first to examine KOR levels and NTX responsivity in FHP and FHN heavy drinkers; this will help us understand if the differential responsivity to NTX observed in FHP and FHN drinkers is related to KOR occupancy by NTX.

[figure not shown]

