Our project will investigate a provocative finding in alcohol treatment research [3]. Namely, that FH of alcoholism may influence (or be a marker of an underlying trait that influences) the response of heavy drinkers (HD) to NTX. Simply put, not every HD responds favorably to NTX but lower levels of drinking can be achieved and risk of relapse is diminished in some. It is essential for clinical treatment and future drug development to understand how NTX works. Preclinical results have implicated kappa in *changes* in alcohol drinking, but the directionality of these changes are complex. We propose that the differential efficacy of naltrexone may be related to differences in occupancy of kappa opioid receptors by naltrexone. This translational project will test this hypothesis. The results of this project could not only help maximize treatment effectiveness of naltrexone but also result in identification of new medication treatment targets for more optimal reduction of alcohol drinking.

3. Research Plan: Provide an orderly scientific description of the study design and research procedures as they directly affect the subjects.

A total of 56 HD subjects will be tested; equal numbers of FHP and FHN subjects will be recruited. Data from the first year's subjects ("initial cohort" perhaps specify how many will be used for this purpose) will be analyzed prior to scanning the remaining subjects in order to address aims S2 and S3 (identification and validation of a reference region; reduction in scan duration) which are addressed below in PET methods.

Study design: Because we are interested in investigating the implications of baseline KOR, as well as Occupancy of KOR by NTX, we must perform 2 PET scans on each subject; one at

baseline and one following 5-11 days of NTX pretreatment. Similarly, because we are interested in relating responsivity to occupancy of KOR by NTX we must make two assessments of drinking behavior using the ADP; one at baseline the day before or after the first PET scan and one following 5-11 days of treatment with NTX. The post PET scan and post ADP will ideally take place on Day 6 or Day 7 of medication, but we will allow up to 11 days of medication for scheduling issues and the possibility that the appointments will be within this time frame. All

In designing the study, we had to balance various competing interests and we provide justifications below:

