- a. Lack of Placebo and use of within subjects design: We considered including a placebo control. But then in order to control for “order” effects, we would have had to randomize placebo and NTX conditions AND allow a significant washout period between medication conditions, especially for those receiving NTX first. This would have led to problems with retention and increased the sample size. We also considered a between subjects design but this would have also increased sample size and costs. Therefore, in order to contain costs and increase feasibility, we decided to use a within subjects design examining a change from baseline, and configured the overall duration of participation to be as close to a single week as possible. While our proposed design could still have “order” effects we do not believe that it will influence our ability to detect an initial signal.
- b. Use of Mock ADP and PET sessions: To minimize the possible stress and novelty associated with a first PET scan and the ADP sessions, as time and scheduling permits, we will conduct a mock PET scan and a walk-through of the ADP procedures prior to the baseline PET and ADP. During the mock PET session, the subject will lie in a replica of the PET scanner, be told when the scanner is being “turned on” and when blood samples are “being drawn”. During the mock ADP session, participants will be exposed to the HRU rooms in YNHH where the ADP’s are conducted and will be walked through the ADP procedures.
- c. Timing of PET scan: The preliminary PET test/retest data suggest that BP_{ND} for our new KOR tracer may be higher in the afternoon (Figure 6). (Note: This *cannot be* explained by a carryover effect of a high-mass injection of tracer in the morning (test) scan, since that would cause BP_{ND} to be lower in the second scan.) We speculate that this effect could be due to diurnal fluctuations in dynorphin level. Regardless, we will control for it by scheduling each scan at approximately the same time of day (around mid-day).

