- l) Psychophysiological Measures: These will include heart rate and blood pressure monitored

using a Critikon Dinamap while skin temperature will be measured using Yellow Springs Instruments 4600 precision thermometer. The cuff of the Dinamap will be on the subject's dominant arm while the probe of will be attached to the middle finger of the subject's non-dominant arm. These data will be further used to examine the safety of using the medication combination during alcohol self-administration.

1) **Cold Pressor Task** (Edens & Gil, 1995): To evaluate the ability of participants to deal with a physiological stressor and to examine pain thresholds in relation to medication effects and drinking behavior. Subjects will be informed that the experimenters are investigating the body's physiological response to cold water during nicotine withdrawal. Subjects will be asked to immerse their right arms into ice water maintained at 3-4°C. Subjects are asked to raise their left hand when they begin to feel pain (pain threshold) and to remove their hand from the water when they can no longer tolerate the pain (pain tolerance). While their hand is immersed in water subjects are also asked to rate their pain on an analog scale of 0-100.

3. **Statistical Considerations:** Describe the statistical analyses that support the study design. Outcomes for this study will be collected using scannable forms (Teleforms). The scanned forms will be processed through the Teleforms software and exported to a database on a secure computer. Error checking and data validation will occur weekly and any problems will be queried and resolved immediately. Drs. [name] will receive monthly data quality reports to check for completeness and accuracy of key demographic and prognostic variables, as well as rates of recruitment, retention, and follow-up. Statistical tests will be conducted using SAS v9.1 and SPSS v16 (or later) and will be performed at 2-tailed alpha level of 0.05

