Primary Aim 1. Occupancy of KOR by NTX and drinking. This aim seeks to determine the degree to which occupancy of kappa by NTX mediates responsivity to NTX in heavy drinkers. Responsivity to NTX is defined as the change in the total number of drinks consumed in the NTX ADP versus the baseline ADP. Tests for mediation will be conducted using the regression strategies described initially Baron and Kenny [53], and the more recent elaboration by Kraemer et al. [54]. The proposed mediator (i.e., the potential mechanism of change), occupancy of KORs, is measured as the fractional change in BP_{ND} before and after treatment with NTX. The analyses will determine whether occupancy is associated with a) NTX treatment, and b) NTX responsivity.

Primary Aim 2. Family History of Alcoholism as a moderator: This aim seeks to determine if the relationship between NTX responsivity and occupancy of KOR is altered by FH status. FHP and FHN will be compared on NTX responsivity and occupancy of KOR. Tests for moderation will be conducted using the strategies described by Baron and Kenny [53], and the elaborated by Kraemer et al. [54]. The primary tests will be whether there is a significant FH by dose interaction on NTX response and occupancy of KOR.

Secondary Aim 1. Baseline KOR differences. This aim seeks to determine if baseline levels of KOR differ between FHP and FHN heavy drinkers, and are related to either drinking in baseline or NTX ADP. FHP and FHN groups will be compared using chi-square tests for categorical variables, and using t-tests or Mann-Whitney tests for continuous variables. All continuous variables will be examined for adherence to the normal distribution using normal probability plots and Kolmogorov-Smirnov tests. If normality is not satisfied and transformations do not help with achieving normality, alternative analytic strategies will be considered such as generalized estimating equations or nonparametric methods. The relationship between baseline KOR and drinking will be examined via Pearson product-moment correlations.

Secondary Aims 2 and 3. Scan duration and reference region. We will look for correlations between BP_{ND} estimates based on 2T model with full AIF and all data vs alternative models and data ranges. Group variances in baseline KOR at or lower than 2T estimates will permit adoption of simpler models.

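### No planned test relates baseline KOR to responsivity: the Secondary Aim 1 analysis puts drinks in the NTX session where aim S1b asks about change

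*Combined protocol and SAP*

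**What the plan says.** The Specific Aims state S1b as: "To determine if baseline KOR level is related to either baseline drinking or responsivity to NTX". The Statistical Considerations, under Primary Aim 1, fix the meaning of the second term: "Responsivity to NTX is defined as the change in the total number of drinks consumed in the NTX ADP versus the baseline ADP". Aim P1 in the Specific Aims defines it in the same way.

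Under Secondary Aim 1, the Statistical Considerations restate the aim as whether baseline KOR levels differ by family history and "are related to either drinking in baseline or NTX ADP". Responsivity is no longer mentioned. The only sentence that names a test is: "The relationship between baseline KOR and drinking will be examined via Pearson product-moment correlations". The Background is equally loose: the study will "correlate KOR levels with drinking in the ADP".

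Nowhere does the protocol plan a correlation of baseline KOR with the change in drinks, or an analysis of NTX-session drinks that takes account of baseline drinks.

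**The concern.** The aim and its analysis name different outcomes. Someone who drinks heavily in both sessions and someone whose drinking rises on NTX can have the same NTX-session count, yet only the second has changed. A correlation of KOR with that count therefore cannot separate a marker of usual drinking from a marker of response.

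The protocol itself treats change as the quantity of interest. In justifying the absence of a placebo, the Research Plan says "we decided to use a within subjects design examining a change from baseline". The section on minimizing risks allows a participant who takes no choice drinks at the first ADP to be discontinued, because change could not then be assessed.

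What is at stake is a claim about who responds to NTX. The protocol's second hypothesis already links positive response to lower baseline KOR, so a significant correlation with NTX-session drinks could easily be reported as support for it.

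**Working it through.** **Plan's own figure.** There is none to reproduce. The power analysis covers the family-history effect on drinking, not S1b.

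**Inputs from the documents.** Tests are two-sided at 0.05 (Statistical Considerations: "will be performed at 2-tailed alpha level of 0.05"). The number of heavy drinkers is given in two ways: 18 + 18 = 36 in the Specific Aims section, and in the Research Plan "A total of 56 HD subjects will be tested". I used both.

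**Assumed inputs, not in the documents.** The correlation ρ of KOR with usual drinking is 0, 0.3, 0.5 or 0.6. The correlation c between sessions is 0.6 or 0.8.

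**Model.** Baseline drinks B = U + e1 and NTX drinks N = U + e2. U is usual drinking with variance c, and each error has variance 1 − c. KOR (K) correlates ρ with U and has no relation to the NTX effect. A constant mean shift on NTX changes no correlation.

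**Expected correlations.**
- corr(K, N) = ρ√c. For ρ = 0.3, c = 0.6 this is 0.3 × 0.775 = 0.23. For ρ = 0.6, c = 0.8 it is 0.6 × 0.894 = 0.54.
- corr(K, N − B) = 0, because U cancels.

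**Rejection rates when KOR does not predict response** (20,000 simulated trials per setting; each range runs over c = 0.6 and 0.8):

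| ρ | n | K with NTX drinks | K with change | K with NTX drinks, adjusted for baseline drinks |
|---|---|---|---|---|
| 0 | 36 | 5% | 5% | 5% |
| 0.3 | 36 | 28–36% | 5% | 8–11% |
| 0.5 | 36 | 66–81% | 5% | 16–23% |
| 0.6 | 36 | 83–94% | 5% | 24–34% |
| 0 | 56 | 5% | 5% | 5% |
| 0.3 | 56 | 41–52% | 5% | 10–14% |
| 0.5 | 56 | 85–94% | 5% | 23–34% |
| 0.6 | 56 | 96–99% | 5% | 35–50% |

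The change score ran from 4.8% to 5.2% throughout. The adjusted analysis is only a partial cure here, because one session measures usual drinking with error.

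**The reverse error.** Take ρ = 0.5, c = 0.7 and a true KOR effect on change of −0.4 drinking SD per SD of KOR. Then cov(K, N) = 0.5 × √0.7 − 0.4 = 0.418 − 0.4 = 0.018, so the two influences nearly cancel. In simulation the correlation with NTX drinks averaged 0.02 and was significant in about 5% of trials. The change score detected the effect in 83% (n = 36) and 95% (n = 56).

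**A model in which the change score is the biased one.** Suppose KOR is unrelated to NTX drinks once *observed* baseline drinks are held fixed, and corr(K, B) = 0.4. With equal variances, corr(K, N − B) = −0.4 × √((1 − c)/2). This is −0.22 at c = 0.4 and −0.15 at c = 0.7, through regression to the mean.

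**Power when KOR is unrelated to baseline drinks.** Assume a baseline-adjusted correlation of 0.45 and equal variances. Then corr(K, N) = 0.45√(1 − c²) and corr(K, N − B) = 0.45√((1 + c)/2). Power by Fisher z:

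| c | NTX drinks: r; power at n = 56, 36 | Change: r; power at n = 56, 36 |
|---|---|---|
| 0.4 | 0.41; 89%, 71% | 0.38; 82%, 62% |
| 0.5 | 0.39; 85%, 66% | 0.39; 85%, 66% |
| 0.7 | 0.32; 68%, 48% | 0.41; 90%, 72% |

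**The case against.** The best defence is that the text is loose rather than wrong. The phrase about the NTX ADP sits in a sentence restating the aim. The sentence that names the test refers only to drinking, and responsivity is defined a few lines above. An analyst could read the correlation as one with change. That is possible, but it is the less literal reading: the same section uses responsivity precisely for Primary Aims 1 and 2, then drops it for Secondary Aim 1. Even on the generous reading the outcome is left unspecified, and the same edit is needed.

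A second defence is that KOR will also be correlated with baseline drinks, so a careful reader would notice if KOR merely tracks usual drinking. This stands in part, because the warning sign would be on the page. But two separate correlations, one significant and one not, do not test whether KOR is related to the difference.

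A third is that the harm depends on conditions the documents do not establish. This stands. With KOR unrelated to usual drinking the false-positive rate is 5%. The protocol does regard the link as plausible: the Background suggests that KOR differences may underlie differences in the propensity to drink, and S1b sets out to test it. Nor do the documents show that drinkers keep their rank order on NTX. The earlier work they cite found lower drinking in one family-history group and higher in the other.

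**Conclusion.** The mismatch is a matter of text and needs no assumption: as written, the second half of S1b has no planned test. Its consequence is conditional. The 28–94% (n = 36) and 41–99% (n = 56) false-positive ranges hold for assumed KOR correlations of 0.3 to 0.6 with usual drinking and session correlations of 0.6 to 0.8. They come from a Gaussian model that ignores the limits of 0 and 12 drinks, and those limits could themselves tie the change score to baseline drinking.

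Two stronger readings should be resisted. A reader might infer that using NTX-session drinks generally costs power. Against the protocol's own change score that is true only when the sessions correlate above 0.5 (last table, where KOR is unrelated to baseline drinks). Below that, NTX-session drinks have more power, and the documents do not give the session correlation. A reader might also infer that the baseline-adjusted analysis should become the main one. The protocol defines responsivity as change, and in the scenario at issue adjustment still rejects falsely in 8–50% of trials. Neither method is unbiased under every model, so the protocol's definition should decide which leads.

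This is half of a secondary aim. The primary aims and the sample size do not depend on it.

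**What to change.** In the Statistical Considerations, Secondary Aim 1, replace drinking in the NTX ADP with responsivity as the protocol defines it. The text could read: baseline KOR will be correlated (i) with drinks in the baseline ADP and (ii) with responsivity, calculated as NTX-ADP drinks minus baseline-ADP drinks; the partial correlation of baseline KOR with NTX-ADP drinks, adjusting for baseline-ADP drinks, will be reported as a sensitivity analysis. State the sign convention, so that a negative change means less drinking on NTX. If the two analyses disagree, report both and say that regression to the mean or measurement error in the baseline session may explain it. The looser Background wording can be aligned at the same time.

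The cost is a sentence or two. Both session counts are already collected, and the change should be made before the S1b results are seen.

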We hypothesize that (1) degree of NTX occupancy of KOR during treatment will be correlated with the degree of responsivity to NTX in all heavy drinkers and (2) FHP heavy drinkers, who respond positively to NTX, will have lower baseline KOR levels when compared with FHN heavy drinkers.

2. **Background:** Describe the background information that led to the plan for this project. Provide references to support the expectation of obtaining useful scientific data.

Alcohol abuse is one of the leading causes of disability in the United States. At present, three medications are approved by the FDA for the treatment of alcohol dependence: disulfiram, naltrexone, and acamprosate. However, the efficacy of these agents ranges from minimal to modest, and they are under-utilized in clinical community settings [6, 7]. There is a pressing need for novel medications that are more effective in reducing alcohol use.

Development of new pharmacotherapeutic approaches to treating alcohol dependence should be based on our understanding of the behavioral and neurochemical mechanisms mediating alcohol drinking, as well the efficacy of agents known to reduce alcohol drinking. Naltrexone (NTX) is a non-specific opioid antagonist that has been shown to have minimal-modest efficacy in treating alcohol dependence. Clinical trials indicate that treatment-seeking heavy drinkers who receive NTX at a dose of 50 mg/day [1, 8] or 100 mg/day [9], have lower levels of relapse to drinking during the treatment period than do those receiving placebo. Subpopulations of alcohol dependent patients may respond better to NTX [10] and family history (FH) of alcoholism is emerging as an important predictor of NTX response [3, 11].

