Our earlier work, using a laboratory-based alcohol drinking paradigm (ADP) revealed that NTX responsivity was altered by the presence or absence of a FH of alcoholism; specifically NTX treatment was associated with lower drinking in those with a positive FH (FHP) and actually with higher drinking in those with a negative FH (FHN) [3]. Developing a better pharmacological understanding of this differential response could help enhance the efficacy of NTX treatment. Naltrexone's ability to reduce alcohol drinking is believed to be mediated, in part, through its effects on the endogenous opioid system, specifically through dose dependent antagonism of mu, delta and kappa opioid receptors. Weerts and colleagues [4] have shown that the most commonly used dose of naltrexone, 50 mg/day, results in almost complete occupancy (saturation) of mu-opioid sites in the brain with variable, partial occupancy of delta opioid receptor sites. This evidence suggests that the differential efficacy of NTX is unlikely to be mediated by mu-opioid binding but could be related to variability in binding to other (delta or kappa) opioid receptor sites. While some investigations have focused on the delta system [4], to date, no one has examined the relationship of kappa opioid receptors (KOR) to alcohol drinking or NTX responsivity in human alcoholics.

Emerging evidence suggests an important, but complex, role for the KOR system in alcohol drinking. Dynorphin is the endogenous opioid ligand that binds to both mu and KORs [12]. In general, activation of KORs is aversive. Animals will not self-administer dynorphin, administration of dynorphin results in conditioned place aversion in animals, and dynorphin

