Auxiliary Aim 1. Kappa and behavioral indicators relevant for alcoholism. This aim will examine the correlations between occupancy of KOR and alcohol craving, stimulation and sedation. A series of Spearman rank-order and Pearson correlation analyses will be conducted for this aim.

Power analysis: The sample size was based on the power calculations for the hypotheses of (a) reduced drinking in the NTX 100 condition, and (b) power to detect an interaction by FH. Power calculations were generated using G*Power software Version 3.0 [55]. Effect sizes were estimated based on the preliminary FH and NTX effects on drinking behavior in the ADP described in [6] and in our preliminary studies. The effect size for the effect of FH is .91. To detect this effect size at $\alpha=.05$ with 80% power, a total of 16 participants would be required for each arm. Therefore the proposed sample size of $n=18$ per arm would be sufficient to detect differences in drinking between FHP and FHN at the 100 mg dose of naltrexone.

SECTION VI: RESEARCH INVOLVING DRUGS, DEVICES, BIOLOGICS & PLACEBOS

Are there any investigational devices used or investigational procedures performed in a YNHH Operating Room? Yes No *If Yes, please be aware of the following requirements:*

- a. A YNHH OR New Product/Trial Request Form must be completed. Please contact the OR Materials Manager, [name], at [contact] for more information on this requirement;
- b. Your request must be reviewed and approved by the Operating Room New Technology Committee before patients may be scheduled; and
- c. The notice of approval from the OR New Technology Committee must be submitted to the HIC for the protocol file.

1. **Identification of Drug, Device or Biologic:** What is (are) the **name(s)** of the drug(s), device(s) or biologic(s) being used? Identify whether FDA approval has been granted and for what indication(s).
Naltrexone is an FDA approved drug that is used in the treatment of alcoholism and opioid addiction.
[C-11]LY2795050 ([C-11]PKAB) PET radiotracer to image kappa opioid receptor, Production of [C-11]LY2795050 ([C-11]PKAB) will be performed with the permission of Yale-New Haven Hospital RDRC

All protocols which utilize a drug, device or biologic **not** approved by, but regulated by, the FDA must provide the following information: **Not applicable to this research project**

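### Secondary Aim 1 correlates baseline KOR with naltrexone-condition drinking without a family-history term, so the correlation can partly restate the family-history difference

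*Combined protocol and SAP*

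**What the plan says.** The list of specific aims states S1b as: "To determine if baseline KOR level is related to either baseline drinking or responsivity to NTX". The Secondary Aim 1 paragraph under Statistical Considerations describes the second drinking variable differently. There, baseline KOR levels are to be examined for whether they "are related to either drinking in baseline or NTX ADP". The method is one sentence: "The relationship between baseline KOR and drinking will be examined via Pearson product-moment correlations". No covariate, stratum or partial correlation is named, and S1b is posed for heavy drinkers without an FH split.

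Elsewhere the plan treats FH as a determinant of both quantities:

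- **Baseline KOR.** The second hypothesis, stated after the aims, is that "FHP heavy drinkers, who respond positively to NTX, will have lower baseline KOR levels when compared with FHN heavy drinkers".
- **Drinking under naltrexone.** The Background reports from the group's earlier work that "NTX treatment was associated with lower drinking in those with a positive FH (FHP) and actually with higher drinking in those with a negative FH". The Power analysis adds: "The effect size for the effect of FH is .91". It ties that figure to the difference in drinking between the FH groups at the 100 mg dose.

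The Research Plan calls for 56 heavy drinkers in equal FH groups. The opening statement of purpose and the Power analysis work with 18 per group. All tests "will be performed at 2-tailed alpha level of 0.05".

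**The concern.** When two groups differ in the mean of both variables, a correlation over the combined sample picks up the difference between groups as well as any relation within them. Here both differences are expected by the plan, and the mix of groups is fixed by recruitment. The KOR difference is already the subject of S1a, and the FH difference in naltrexone response belongs to P2. A significant pooled correlation could therefore repeat those two results while being read as a third, separate finding that receptor level predicts response.

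This matters because KOR as an individual-level predictor of response is a different scientific claim from KOR as something that differs by family history. The planned statistic cannot tell the two apart.

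**Working it through.** **Inputs.** Two-sided alpha 0.05 (Statistical Considerations). Two equal FH groups, 18 each (n=36) or 28 each (n=56); both sizes appear in the plan, so both are used. FH shift in drinking under naltrexone: d2 = 0.91, read as Cohen's d (Power analysis). FH shift in baseline KOR: d1, direction given but size not, so assumed at 0.3, 0.5 and 0.91 SD.

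**The plan's own figure.** The Power analysis gives 16 per arm for an effect of .91 at 80% power. A two-sample t-test with d = 0.91 needs 15.7, so 16 per arm, one-sided, and 19.96, so 20 per arm, two-sided. The stated 16 is reproduced only one-sided. That fits reading .91 as a standardised mean difference. The mismatch with the two-tailed rule is a separate matter.

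**Pooled correlation with no relation inside either group.** For two equal groups,

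r = (d1·d2/4) / √[(1 + d1²/4)(1 + d2²/4)]

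- d1 = 0.3: 0.06825 / √(1.0225 × 1.2070) = 0.061
- d1 = 0.5: 0.11375 / √(1.0625 × 1.2070) = 0.100
- d1 = 0.91: 0.2070 / 1.2070 = 0.172

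For drinking in the naltrexone session the sign is positive, because the FH-positive group is expected to be low on both. For responsivity the sign depends on how the change is coded.

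**How often it is significant.** By Fisher's z, the test statistic is centred at atanh(r)·√(n−3). For d1 = 0.91 and n=56 this is 0.1737 × 7.280 = 1.26, and P(Z > 1.96 − 1.26) is about 24%. For d1 = 0.5 it is 0.1008 × 7.280 = 0.73, giving about 11%. Simulating 40,000 trials per case gives:

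| Assumed KOR shift (SD) | Pooled r | Significant, n=36 | Significant, n=56 |
|---|---|---|---|
| 0.3 | 0.06 | 6.6% | 7.4% |
| 0.5 | 0.10 | 9.0% | 11.5% |
| 0.91 | 0.17 | 17.0% | 25.2% |

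With FH in the model, the rate is 4.9-5.1% in every one of these cases.

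**Baseline drinking.** The documents state no FH effect on drinking in the baseline session. Setting d2 = 0 makes r = 0 for every d1, and the simulated pooled rate stays at about 5%.

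**The case against.** The strongest reply is that S1b asks only whether KOR is related to drinking or response. That is a marginal association, and a Pearson correlation answers it. If FH shifts both variables, the marginal correlation truly is nonzero, and detecting it is not an error for that question. The plan also suggests that KOR differences may underlie the FH difference in response (opening statement of purpose) and may mediate differential responsivity (Background). If so, the between-group part is some of the signal, and conditioning on FH removes it. This stands. It rules out the reading that FH is established as a common cause and that the pooled correlation must be discarded. The Background itself allows that FH may only mark an underlying trait.

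Several other limits also stand:

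- A reader might infer that both S1b correlations are affected. The one with baseline drinking is not, on anything the documents say.
- The .91 is given for drinking at 100 mg, not for the change score that defines responsivity. Carrying it over to responsivity is an assumption.
- The KOR shift is assumed, and at 0.3 SD the excess over 5% is small.
- Pooling is inferred from silence, although a plain Pearson correlation has no place for FH.
- S1a and P2 will be reported alongside, which gives an attentive reader some protection.

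None of this lets the pooled coefficient separate KOR as a predictor from KOR as a marker of FH.

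**Conclusion.** The point holds for the naltrexone half of S1b: baseline KOR against drinking in the naltrexone session, or against responsivity. Under the plan's own hypotheses and with no within-group relation, the expected pooled r is about 0.10 to 0.17. The chance of a significant result is then about 11-25% at n=56 and 9-17% at n=36, against about 5% with FH adjusted for. These figures rest on .91 being Cohen's d, on its applying to the outcome used, and on an assumed KOR shift of 0.5 to 0.91 SD.

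It would be too strong to say that a spurious correlation will appear. Even at the upper end of that range, about three trials in four would show no significant result. This is a secondary aim with no power claim attached, but the gap is real and cheap to close.

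**What to change.** In the Secondary Aim 1 paragraph, keep the pooled Pearson correlation and label it the marginal association. Add a regression (or partial correlation) of the naltrexone-condition outcome on baseline KOR with FH group as a covariate, and show the slope within each FH group. State that any conclusion that KOR predicts response beyond family history rests on the FH-adjusted coefficient. The same edit should name one naltrexone-condition outcome, since the aims list responsivity and the statistical section lists drinking in the naltrexone session.

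The cost is a few lines of text and one degree of freedom. FH is assessed at intake, so no new data are needed. The adjusted estimate leaves out any part of the FH effect that runs through KOR, which is why both estimates should be reported.
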